9.9.1. Primary Patency Analysis

The primary endpoint will be the cumulative incidence of primary patency at 9-months of study computed as the number of subjects with primary patency at 9-months divided by the number of subjects in the ITT population. An exact binomial one-sided 95% confidence interval will be constructed and the upper limit compared to the Performance Goal equal to 70%. A p-value for the one-sided exact test of the difference between the observed rate and the Performance Goal will be presented. The primary analysis will be analyzed with observed data only.

A planned subgroup analysis of the primary functional endpoint will be performed (details are provided in section 9.9.4

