4. STUDY OBJECTIVES

The primary objective of this study is to assess the safety and efficacy of the iCAST™ RX Stent System in subjects with resistant hypertension associated with de novo atherosclerotic renal artery disease. The primary objective will be evaluated using co-primary endpoints. The primary functional endpoint will assess safety and effectiveness based on the primary patency rate at 9-months on a per lesion basis evaluated against a performance goal of published studies with bare-metal stents. The primary clinical endpoint will assess the improvement in Systolic Blood Pressure (SBP) at 9-months as compared to baseline SBP.

The secondary objectives of this study are:

- 1) To evaluate the occurrence of procedure-related Major Adverse Events (MAEs) reported as percentage of subjects with MAE, at 30-days, 9-months, 12-months, 24-months, and 36-months.
Inclusive of:
 - i) Procedure-or device-related occurrence of death
 - ii) Q-Wave myocardial infarction (MI)
 - iii) Clinically driven target lesion revascularization (TLR)

Amendment #1: 15Jul13

Confidential

- (1) Defined as a TLR (Percutaneous Balloon Angioplasty (PTA), bare metal stent or repeat covered stent deployment, or surgical bypass) due to documented recurrent hypertension from 30-days post-procedure level and/or deterioration in renal function from baseline value, associated with angiographic core laboratory adjudication of a \geq 60% diameter covered stent restenosis.
- iv) Significant embolic events
 - (1) Defined as unanticipated kidney/bowel infarct clinically driven by symptoms of abdominal or back pain and confirmed with Computed Tomography (CT) scan or open surgery, lower extremity ulceration or gangrene, or kidney failure after 30-days, 9-months, 12-months, 24-months, and 36-months.

MAEs were reviewed and adjudicated by the Clinical Event Committee. The adjudicated data will be used to perform the analysis of this endpoint.

- 2) To determine technical success defined as successful delivery and deployment of the iCAST™ RX Stent System with \leq 30% residual angiographic stenosis after covered stent deployment (including post-dilatation) assessed via Qualitative Vascular Analysis (QVA) by an independent core laboratory.
- 3) To determine acute procedural success defined as technical success without the occurrence of MAE prior to hospital discharge.

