5.2 Discussion of Endpoint Determination

The primary functional endpoint of primary patency has been established since the clinical care

Amendment #1: 15Jul13

Confidential

of the physician is considered a more objective measurement of stent performance than the restenosis measurement of DUS alone. In standard practice, a DUS is used to determine patency of a stent. If a DUS is negative and the subject is asymptomatic, no intervention is typically conducted by a physician. If a subject is symptomatic or a DUS is positive, a confirmatory angiogram is typically performed to assess the patency of the vessel.

To properly match the functional outcomes with historical data, the endpoint will be calculated on a per lesion basis. This reflects the current standard of care of treating subjects with single vessel renal artery lesions and those subjects with bilateral renal artery stenosis. Analysis of past studies has demonstrated that the number of lesions treated per subject has increased with time. A recent renal trial reported 1.2 lesions per subject were treated.

The primary clinical endpoint of reduction in SBP has been established to determine the benefit of revascularization therapy to perfuse the kidney. The Framingham Heart Study showed that decreasing SBP by 10mmHg can be lifesaving. Additionally, Joint National Committee VII (JNC VII) estimates that a 5mmHg reduction in SBP would reduce the incidence of stroke in subjects by 14%, coronary heart disease (CHD) by 9%, and overall mortality by 7%. JNC VII also presented data from a UK diabetes study that demonstrated a 10mmHg decrease in SBP was associated with average reductions of 15% for diabetes-related mortality, 11% for MI, and 13% for microvascular complications of retinopathy or nephropathy.

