5.7 Statistical Hypothesis

Functional endpoint

For the primary patency endpoint, the proportion of subjects-lesion (arteries) experiencing this outcome will be compared to the predefined Performance Goal of 0.70. Formally, the hypothesis to be tested is:

H_0 : The incidence pPP of primary patency at 9-months is less than or equal to 0.70.

$$H_0: pPP \leq 0.70$$

H_A : The incidence pPP of primary patency at 9-months is greater than 0.70.

$$H_A: pPP > 0.70$$

Primary Clinical Endpoint

For the SBP endpoint, the change between SBP from baseline to 9-month follow-up will be compared to a predefined Performance Goal of 10mmHg. Formally, the hypothesis to be tested is:

H_0 : The mean difference between SBP at 9-months and baseline, $\mu\Delta\text{SBP}$, is less than or equal to 10mmHg.

$$H_0: \mu\Delta\text{SBP} \leq 10\text{mmHg}$$

H_A : The mean difference between SBP at 9-months and baseline, $\mu\Delta\text{SBP}$, is greater than 10mmHg.

$$H_A: \mu\Delta\text{SBP} > 10\text{mmHg}$$

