7.6 Endpoints, Safety Outcomes and Other Parameters

7.6.1.Primary Endpoints

Primary Patency Rate

In order to mitigate the challenges with DUS interpretation, clinical validation through independent noninvasive core laboratory and/or angiography will be performed in order to correctly validate and definitively assess percent diameter stenosis. DUS is highly reliable in identifying widely patent stents – however, correlation studies of DUS with angiography have confirmed that DUS is not as accurate when results suggest a stenosis. To lessen the risk of inaccurate readings, if a stenosis is detected in DUS (RAS > 60%) or if the DUS is non-diagnostic due to an imaging quality problem then a contrast angiogram will be used to assess the degree of restenosis of the covered stent(s) at the 9-month visit (± 30 days).

The primary efficacy variable is the primary patency rate, defined as continuous patency without the occurrence of a total occlusion (complete obstruction or a closure of a passageway or vessel determined by DUS or contrast angiogram) of the original lesion, and

Amendment #1: 15Jul13

Confidential

- without a re-intervention due to a clinically driven restenosis or occlusion to treat a partial or total occlusion of the stented segment,
- or bypass of the stented segment due to clinically-driven restenosis or occlusion

The primary patency will be calculated on a per lesion basis – for purpose of analysis in cases in which multiple lesions are covered by one stent then the stented segment will be considered as one lesion. The cumulative incidence of patency at 9 months will be computed as the number of lesions that met primary patency divided by the number of subject-lesions for the population being analyzed.

Change from Baseline in Systolic Blood Pressure

Systolic blood pressure will be assessed at each follow-up study visit. Blood pressure measurements will be obtained with a certified, calibrated, and validated equipment. Subjects will be instructed to refrain from exercise, smoking or caffeine ingestion for 30 minutes before blood pressure measurement, and measurements will be obtained after at least 5 minutes of rest. At each time point, a minimum of three (3) readings separated by 2 minutes will be averaged.

The primary clinical outcome is the improvement in systolic blood pressure (SBP) at 9-months as compared to baseline systolic blood pressure computed as follows:

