8.8 Unit of Analysis

For the primary functional endpoint of primary patency rate the unit of analysis is the atherosclerotic lesion(s). The rationale for analyzing the primary endpoint following a per lesion approach, is to avoid overestimation of the failure rate, as more lesions would be at risk for restenosis but would not be accounted for in a per subject analysis.

Since blood pressure is measured on the subject level, the primary clinical endpoint of change SBP will be evaluated at the subject level.

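### SAP 9.9.1 counts primary patency by subject against the plan's own lesion unit, and compares the wrong confidence limit, at the wrong level, with the 70% goal

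*SAP*

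**What the plan says.** **Unit.** SAP 9.9.1, the section that specifies the primary patency analysis, gives the rate as "computed as the number of subjects with primary patency at 9-months divided by the number of subjects in the ITT population". Elsewhere the SAP says otherwise:

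- SAP 4 assesses "the primary patency rate at 9-months on a per lesion basis".
- SAP 5.2 gives the reason: "To properly match the functional outcomes with historical data, the endpoint will be calculated on a per lesion basis".
- SAP 5.7 states the hypothesis for lesions: "the proportion of subjects-lesion (arteries) experiencing this outcome will be compared to the predefined Performance Goal of 0.70".
- SAP 7.6.1 gives a competing formula, "computed as the number of lesions that met primary patency divided by the number of subject-lesions for the population being analyzed".
- SAP 8.8, the section on the unit of analysis, names the lesion and says this avoids overestimating failure.

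The mixed wording goes back to the protocol. Protocol 2.1 is per lesion, while protocol 5.1 and 5.2 (and SAP 5.5) speak of subjects.

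**Denominator.** The formula names the whole ITT population, yet the same paragraph adds "The primary analysis will be analyzed with observed data only".

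**Interval.** SAP 9.9.1 continues: "An exact binomial one-sided 95% confidence interval will be constructed and the upper limit compared to the Performance Goal equal to 70" per cent. Protocol 5.3.5.1 says the same. The alternative hypothesis in SAP 5.7 is patency greater than 0.70. SAP 5.5 and 9.9 set the level at one-sided 0.025.

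**The concern.** Two analysts who follow the SAP could report different primary rates. SAP 9.9.1 also gives no rule for when a subject with two treated lesions counts as patent.

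The interval comparison fails on direction and on level. To support a rate above 70%, the lower limit must exceed 70%. An upper limit above 70% only fails to exclude rates above 70%, and an upper limit below 70% would show the opposite of what the trial seeks. A one-sided 95% limit corresponds to alpha 0.05, not 0.025. The same sentence has the right direction for target lesion revascularization in SAP 9.10.1, where a low rate is the goal.

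At stake are the reported patency rate and the sentence that sets it against 70%.

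**Working it through.** **Inputs.** Goal 0.70, assumed patency 0.82, one-sided alpha 0.025, 125 evaluable, at most 27 failures, power 87% (SAP 5.5); 68 subjects enrolled (SAP 6.1). The number of lesions is not given. For illustration I take the 1.2 lesions per subject that SAP 5.2 cites from another trial: 68 × 1.2 = 81.6, say 82 lesions, so 82 − 68 = 14 bilateral and 54 unilateral subjects.

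**Formulas.** For x patent of n: p = P(X ≥ x) with X binomial(n, 0.70). Exact lower limit = beta quantile at α with parameters x and n−x+1. Exact upper limit = beta quantile at 1−α with parameters x+1 and n−x.

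**1. The plan's own figure.** 125 − 27 = 98.

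- 98/125 (78.4%): p = 0.023, lower 97.5% limit 0.7015, power at 0.82 = 0.876. This reproduces SAP 5.5.
- 97/125 (77.6%): p = 0.037, lower 97.5% limit 0.6928, lower 95% limit 0.7060.

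The 27-failure mark is therefore the lower 97.5% limit. A lower 95% limit would admit a 28th failure.

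**2. The limit named in SAP 9.9.1.** The one-sided 95% upper limit exceeds 0.70 from 79/125 (63.2%, limit 0.7040). At a true rate of exactly 70% that happens with probability 0.96. With 82 lesions:

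| Limit set against 70% | First count above 70% | Limit | p |
|---|---|---|---|
| Upper 95% (SAP 9.9.1) | 50/82 = 61.0% | 0.7003 | 0.97 |
| Lower 95% | 65/82 = 79.3% | 0.7054 | 0.040 |
| Lower 97.5% | 66/82 = 80.5% | 0.7026 | 0.022 |

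Only the last row agrees with p < 0.025.

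**3. The unit.** Suppose nothing is missing and a subject is patent only if every treated lesion is (an assumption).

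- 13 failed lesions in 13 subjects: 69/82 = 84.1%, p = 0.0025 per lesion; 55/68 = 80.9%, p = 0.030 per subject.
- 16 failed lesions in 16 subjects: 66/82 = 80.5%, p = 0.022; 52/68 = 76.5%, p = 0.15.
- The same 16 failures paired in 8 bilateral subjects: 60/68 = 88.2% per subject, so the direction reverses.

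On average, at 82% lesion patency and within-subject correlation r, P(both patent) = 0.82² + r × 0.82 × 0.18. The subject rate is (54 × 0.82 + 14 × P(both patent))/68 = 79.0%, 80.5% and 81.4% at r = 0, 0.5 and 0.8. The gap is 3.0, 1.5 and 0.6 points. With 7 bilateral subjects it halves to 1.5, 0.8 and 0.3, and with none it is zero.

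**4. Clustering.** The exact binomial treats lesions as independent. At p = 0.70, give each bilateral pair P(both patent) = 0.7² + r × 0.21 and P(both failed) = 0.3² + r × 0.21. Add 14 such pairs to 54 single lesions and take P(at least 66 patent). The true one-sided error of the 66/82 rule is 0.022 at r = 0, 0.032 at r = 0.5 and 0.038 at r = 0.8.

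**The case against.** The strongest case against is that this is a wording slip with little consequence. SAP 8.8 is devoted to the unit and SAP 7.6.1 gives the full lesion formula, so a careful analyst would probably use lesions. SAP 9.9.1 keeps a one-sided exact p-value, and SAP 8.1 displays two-sided 95% exact intervals whose lower bound is the right one. SAP 2, 6.2 and 8.7 make all inference descriptive after enrollment stopped.

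Most of this stands and limits the weight of the point. It does not remove a rule that is wrong as written: SAP 9.9 and 9.9.1 keep the 0.025 threshold and the comparison with 70%, and the paragraph names the wrong limit, the wrong level and a unit that five other sections contradict.

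A reader might infer more in three ways. The documents do not support them:

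- **That a patency rate near 61% would be declared a success.** SAP 9.9.1 says only that the limit is compared, not that exceeding 70% means success, and the p-value beside it would be 0.97.
- **That counting subjects systematically biases the result.** The reversals in step 3 need every failure in a different subject, and the sign changes if failures are paired. At 12 such failures both units pass (56/68, p = 0.015).
- **That omitting the protocol's tipping-point analysis is an error.** SAP 2, 6.2 and 8.3 declare and explain that change. SAP 7.2 also refers 9-month data handling to a data management plan that is not among the documents and may settle the denominator.

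**Conclusion.** The point holds for the reported estimate and its stated comparison with 70%; no confirmatory decision rests on it. That the limit and level are wrong follows from the plan's own figures: 27 failures in 125 matches the lower 97.5% limit and no other. The contradiction over the unit is plain in the text. Its numerical effect rests on assumed bilateral counts and correlation: 0.3 to 3.0 points on average in the cases tried, zero if no subject had two lesions treated. It should be fixed before the analysis is reported.

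**What to change.** 1. Rewrite SAP 9.9.1 as patent lesions over ITT lesions with observed 9-month status, counting any earlier failure under SAP 7.6.1 as a failure.
2. Compare the lower limit of the one-sided 97.5% exact interval with 70%. This is the lower bound of the two-sided 95% interval already planned in SAP 8.1.
3. Change the one-sided 95% interval that SAP 8.1 plans for subgroups to match.
4. Record unit, limit and level in SAP 6.2 as changes from protocol 5.1, 5.2 and 5.3.5.1.
5. State that the exact lesion-level interval and p-value assume independent lesions, and add a subject-clustered interval as a check.

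Optional: restore the protocol's tipping-point table, and define the event for the supportive time-to-event analysis in SAP 7.4.

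The cost is one rewritten paragraph, short edits to SAP 8.1 and 6.2, and one added interval, with no new data. There are two downsides. The 97.5% limit asks for one more patent lesion than a lower 95% limit would (66 instead of 65 of 82). Keeping early failures while dropping early withdrawals also lowers the rate slightly: with 18% true failure at constant hazard and 10% uniform dropout, observed failure is (0.9 × 0.18 + 0.1 × 0.093)/(0.9 + 0.1 × 0.093) = 18.8%, where 0.093 is the chance of failing before dropping out.

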9.9.2. Systolic Blood Pressure Analysis

The primary endpoint of SBP will be analyzed according to the Performance Goal of a decrease in SBP of 10mmHg.

The mean difference between SBP at 9-months and baseline will be compared to a fixed value of 10mmHg. The baseline and 9-month SBP data, as well as the difference in baseline will be summarized with means and standard deviations. A one-sided 95% confidence interval for the mean difference between baseline and 9-month SBP will be constructed and the upper limit will be compared to the 10mmHg Performance Goal. A p-value of the difference between the estimated SBP change from baseline and the Performance Goal will be computed using a paired t-test.

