2. DEVIATIONS FROM THE PROTOCOL

Due to the early termination of enrollment for the Protocol/CIP No. iCAST™ RX-ARAS-001 in November 2017, all inferential analysis should be interpreted as descriptive and will be carried out in an exploratory manner.

Missing data will not be imputed for analysis purposes as there is no need to evaluate the robustness of the primary analysis or the impact of missing data.

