5.5 Determination of Sample Size

For a one-sided alpha of 0.025 and desired power of 87%, sample size for the primary patency endpoint is established by assuming a hypothesized primary patency incidence of 0.82, which

Amendment #1: 15Jul13

gives 125 evaluable subjects therefore, accounting for 10% attrition, 138 subjects are needed for this endpoint. At the proposed evaluable sample size of 125, no more than 27 subjects (22%) can fail primary patency in order to meet the endpoint hypothesis.

For the endpoint of reduction in SBP, we assume an average reduction of 13.7mmHg. Under a hypothesized standard deviation of 12mmHg for a difference in SBP there will be 92% power to meet the Performance Goal. This standard deviation is conservatively approximated based on the expected range of SBP at baseline of 155mmHg to 180mmHg divided by 3 and assuming a similar standard deviation at the 9-month follow up. A mean difference in SBP at 9-months of 12mmHg will be required in order to reject the null hypothesis at a one-sided alpha of 0.025 at the proposed sample size.

The primary endpoints of primary patency and reduction in SBP are powered at 87% and 92%, respectively, in order to maintain the overall trial power at 80% to meet both endpoints.

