6. CHANGES IN THE CONDUCT OF THE STUDY OR PLANNED ANALYSES

6.1 Changes in the Conduct of the Study

The enrollment for Protocol/CIP No. iCAST™ RX-ARAS-001 has been terminated after 68 subjects were screened and enrolled in the study as of November 2017. Enrolled subjects will be followed up to study completion.

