$$\text{SBP change from baseline} = (\text{SBP value at 9-months} - \text{SBP value at baseline})$$

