9.9 Analysis of Primary Endpoints

Statistical tests relating to the primary endpoints will be one-sided with p-values less than 0.025 deemed significant.

Amendment #1: 15Jul13

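### The SBP co-primary test has no consistent sign across SAP 5.7, 7.6.1 and 9.9.2, and its one-sided 95% interval does not match the one-sided 0.025 test

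*SAP*

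**What the plan says.** - **Goal in words.** SAP 9.9.2 analyses SBP "according to the Performance Goal of a decrease in SBP of 10mmHg".
- **Endpoint formula.** SAP 7.6.1 subtracts the baseline value from the 9-month value, so a fall in SBP is negative. SAP 7.6.2 (item 6) and 9.11.7 use the same order of subtraction.
- **Hypotheses.** In SAP 5.7 the alternative is that the mean 9-month versus baseline difference "is greater than 10mmHg". No minus sign appears and the order of subtraction is not given. Protocol 5.1 has the same form.
- **Decision rule.** SAP 9.9.2: "A one-sided 95% confidence interval for the mean difference between baseline and 9-month SBP will be constructed and the upper limit will be compared" with the 10 mmHg goal. The 10 is unsigned, the two time points are named in both orders within the section, and nothing says whether the limit must fall above or below 10. Protocol 5.3.5.2 does not name the side of the limit; the SAP added that it is the upper one.
- **Level.** SAP 9.9: "Statistical tests relating to the primary endpoints will be one-sided with p-values less than 0.025 deemed significant". Protocol 5.1 also sets one-sided 0.025.
- **Planning values.** SAP 5.5: "we assume an average reduction of 13.7mmHg". The SD of the difference is 12 mmHg, the stated power is 92%, and an observed difference of 12 mmHg is said to be needed to reject.
- **Status.** SAP 6.1 reports that enrollment "has been terminated after 68 subjects were screened and enrolled", and SAP 2 adds that "all inferential analysis should be interpreted as descriptive".

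**The concern.** The formula, the hypothesis and the decision rule for one co-primary test have to share a sign convention, and here they do not.

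On the SAP 7.6.1 scale, benefit is a negative number. The upper limit is then the right bound, but it has to be compared with -10, a value the SAP never prints. On a reduction scale (baseline minus 9-month), the SAP 5.7 alternative is right, but success then requires the lower limit to exceed 10. Pairing an upper limit with positive 10 gives no valid rule for showing a fall of more than 10 mmHg on either scale.

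A second defect does not depend on sign. A one-sided test at 0.025 corresponds to a one-sided 97.5% limit. A one-sided 95% limit corresponds to 0.05, so the interval and the p-value can give different answers on the same data.

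The SAP still plans the p-value, the 0.025 threshold and the comparison with the goal. A programmer working from 7.6.1 and 5.7 would test the wrong tail. One working from 9.9.2 with positive 10 could record the goal as met without any fall in blood pressure.

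**Working it through.** **Inputs.** Mean reduction 13.7 mmHg, SD of the difference 12 mmHg, 125 evaluable subjects, one-sided alpha 0.025 (SAP 5.5); goal 10 mmHg (SAP 9.9.2); 68 enrolled (SAP 6.1). The n = 68 figures assume that every enrolled subject has a 9-month SBP and that the SD is 12.

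SE = 12/√n, which is 1.0733 at n = 125 and 1.4552 at n = 68. Critical values: t(0.95, 124) = 1.6572; t(0.95, 67) = 1.6679; t(0.975, 67) = 1.9960.

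**1. The plan's own figures.** Paired t-test on the reduction scale against 10, n = 125, alpha 0.025:
- Power from the noncentral t with noncentrality (13.7 - 10)/1.0733 = 3.447: 92.8%, against the stated 92%.
- Smallest observed reduction that rejects: 10 + t(0.975, 124) × 1.0733 = 12.12 mmHg, against the stated 12.

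Both agree on the reduction scale at 0.025. That identifies the intended test and shows the power calculation is not at fault.

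**2. SAP 7.6.1 and 5.7 taken literally** (9-month minus baseline, alternative above positive 10), with an observed change of -13.7:
- n = 125: t = (-13.7 - 10)/1.0733 = -22.08.
- n = 68: t = -23.7/1.4552 = -16.29.
- One-sided p is about 1.0 in both cases.

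The intended test on the same data:
- n = 125: t = 3.7/1.0733 = 3.447, p = 0.0004.
- n = 68: t = 3.7/1.4552 = 2.543, p = 0.007.

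**3. SAP 9.9.2 with the upper limit and positive 10.** The success side is not stated, so both readings are shown.
- *9-month minus baseline, upper 95% limit below positive 10.* Met when the observed change is below 10 - 1.6572 × 1.0733 = 8.22 (n = 125) or 10 - 1.6679 × 1.4552 = 7.57 (n = 68). No change meets it, and so does a mean rise up to those values. If SBP truly rose by 5 mmHg, the rule would be met with probability 0.999 (n = 125) or 0.960 (n = 68).
- *Baseline minus 9-month, upper 95% limit above 10.* Met by observed reductions above the same 8.22 or 7.57 mmHg, which are short of the goal. At a true reduction of exactly 10, the boundary of the null, it is met with probability 0.95.

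**4. Level mismatch alone, signs corrected.** The goal is met when the observed reduction exceeds 10 + t × SE:

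| n | one-sided 95% limit | one-sided 97.5% limit | power at 13.7 (95% / 97.5%) |
|---|---|---|---|
| 125 | 11.78 | 12.12 | 96.3% / 92.8% |
| 68 | 12.43 | 12.90 | 80.8% / 70.7% |

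An observed reduction between the two thresholds clears 10 by the planned interval but has p between 0.025 and 0.05.

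**The case against.** The strongest reply is that the direction is plain. The endpoint is described as an improvement, the goal as a decrease, and the sample-size section treats a reduction as positive and gives a 12 mmHg rejection threshold at one-sided 0.025. If the goal in SAP 9.9.2 is read as a change of -10, its upper limit is correct under the 7.6.1 formula, and only SAP 5.7 is out of line. On this view the readings in step 3 are hypothetical, and the wrong-tail result in step 2 would be noticed at once. Inference is descriptive, SAP 8.7 drops type I error control, and the reported means would show the direction anyway. The level mismatch matters only in a band of about 0.5 mmHg at n = 68.

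Much of this stands. The intent is recognisable, the extreme readings show ambiguity rather than a likely report, and the consequence is limited. It does not repair the text. The value -10 appears nowhere, so the charitable reading requires the analyst to supply it. Even then SAP 5.7 contradicts 7.6.1, and the repetition of that subtraction in 7.6.2 and 9.11.7 sharpens the clash. Intent also cannot settle whether the interval should be 95% or 97.5%.

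**Conclusion.** The concern holds. SAP 5.7, 7.6.1 and 9.9.2 cannot all be followed under one sign convention, and the interval level in 9.9.2 does not match the test level in 9.9. This is an internal contradiction in the decision rule; the plan does not intend to define success as a rise in SBP.

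The sign conflict can move the p-value from 0.007 to about 1 at n = 68 on the planning values. The level mismatch affects only the narrow band in step 4. All sizes assume SD 12, and those at n = 68 assume complete 9-month data; with no imputation planned, the analysed number can only be lower. Because the analysis is now descriptive, this should be fixed but does not undermine a confirmatory conclusion.

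**What to change.** Use one convention in SAP 5.7, 7.6.1 and 9.9.2. Two equivalent forms:

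- **Option A.** Reduction = baseline minus 9-month. H0: mean reduction ≤ 10; HA: mean reduction > 10. Goal met if the lower one-sided 97.5% limit exceeds 10.
- **Option B.** Change = 9-month minus baseline. H0: mean change ≥ -10; HA: mean change < -10. Goal met if the upper one-sided 97.5% limit is below -10.

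Option B leaves the formulas in 7.6.1, 7.6.2 and 9.11.7 untouched. Under either option, run the paired t-test in the matching tail, state the success side explicitly, and label the result descriptive as in SAP 6.2. Both keep the planned alpha and reproduce the stated power.

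The cost is SAP wording and a check of the program; no new data are needed. Protocol 5.1 and 5.3.5.2 should ideally be aligned, but protocol 8.2 requires a signed amendment submitted to the IRB/EC. If that is impractical now that enrollment has ended, a SAP clarification is enough.
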